6.2.4. Baseline and Change from Baseline

Unless otherwise specified, the baseline value is defined as the last non-missing value prior to the first dose of study drug.

Change from baseline is defined as the difference between the post-baseline assessment value and the baseline value, i.e., Post-baseline Assessment Value – Baseline Value.

6.2.5. Study Day

Day 1 is defined as the day of the first dose of study drug. Relative study days after Day 1 are calculated as (Assessment date – Date of Day 1 + 1). Relative study days prior to Day 1 are calculated as (Assessment date – Date of Day 1). The day prior to Day 1 is Day -1. There is no Study Day 0.

6.2.6. Treatment Exposure

6.2.6.1. Exposure Duration

Subject exposure data are not collected on the study electronic case report form (eCRF). Rather they come from 2 external sources:

- Study drug_accountability (in-clinic) data from Suvoda IRT system.
- Subject daily dosing diary data (non-clinic data) via mobile application (mApp) managed by AiCure. This data will be sent directly to Alladapt for exploratory analysis and are not planned to be included in the CSR of this study

The main calculation of exposure will be based on in-clinic dosing data and the dose level of the dispensed study drug from Suvoda IRT system.

Exposure Duration: Overall Treatment Period

The overall exposure duration (in days) is defined as [Last dose date of treatment – First dose date of treatment + 1].

A combination of the data from the EOT eCRF and the dose information from Suvoda IRT will be used to determine the date of last dose of treatment. For analysis purposes, the date of last study drug administration on the EOT eCRF will be used as the analysis date of last dose date.

Exposure Duration: By Dose Level

At each dose level within the treatment period, the exposure duration (in days) is defined as [Last Dose Date – First Dose Date + 1]. For any subject who has non-continuous dosing at the same dose level due to down dosing, the durations of the individual non-continuous intervals of such dosing are defined as [Last Dose Date of Interval – First Dose Date of Interval +1]. The exposure in days for such subjects at a given dose level would be the sum of the lengths of the individual non-continuous dosing intervals in days for all such non-continuous dosing.

Exposure Duration: Pre-maintenance

The exposure duration of pre-maintenance is anticipated to be of variable length depending on how quickly subjects are able to reach their randomized target dose or maintenance dose.

The exposure duration of pre-maintenance dosing (in days) is defined as [(The day prior to first dose of the sequence of maintenance doses administered closest to the first Exit Food Challenge/Week 40 Visit assessment) – (First dose date of treatment from Baseline Visit) + 1].

Exposure Duration: Maintenance

The exposure duration of the maintenance dosing is defined as [(Date of last maintenance dose before the Exit Food Challenge/Week 40) - (Date of first dose of the sequence of maintenance doses administered closest to the first Exit Food Challenge/Week 40 Visit assessment) + 1].

Exposure Duration: Exit Food Challenge/Week 40

The exposure duration of the Exit Food Challenge/Week 40 dosing (during the treatment period) is defined as [(Date of last dose during Exit Food Challenge/Week 40) - (Date of first dose during Exit Food Challenge/Week 40) + 1].

Exposure Duration: EOT

The exposure duration of the EOT dosing (during the treatment period) is defined as [(Date of last dose during the EOT) - (Date of first dose during the EOT) + 1]. The date of last dose will be the date of last study drug administration on the EOT eCRF.

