Abbreviated PE (Section 8.2.1)		X	X				X*	X	Note: To be done pre-updosing. * If clinically indicated. At Screening and Week 40 prior to each DBPCFC in the series (except the first DBPCFC in each series)
Subject daily diary		←===== Daily completion=====→							The diary is intended to capture dose compliance and dosing-related symptoms that may occur.

Note: Refer to Appendix 6	(Section 10.	6) for guid	ance regarding	study as	sessments a	nd pr	ocedur	es duri	ng public health emergency.
			Treatment F	atment Period					Notes
Procedure	Screening*	Day1/BL	Week 2–38‡ (every 2 weeks)	Week 40#	ЕОТ	ЕТ	UNS&	FU^	*Screening will be done over multiple visits. †When a subject completes updosing, every other visit can occur over the telephone.
Visit window	≤ 12 weeks before Day 1	NA	±4 days	-2 days to +6 weeks	Up to +4 weeks from last Exit DBPCFC	NA	NA	±5 days	*Week 40 visit can be done over multiple visits over 6 weeks to accommodate multiple Exit DBPCFCs. This period may be extended to up to 8 weeks if a subject requires > 6 food challenges. *Unscheduled visit as clinically indicated. ^Follow-up visit will be 14 days post-EOT, only for subjects who will not continue to the OLE.
PRO for accidental exposure (when it occurs)					-				
Study drug administration		←====Oı	ral daily dosing=	===→	X^+		X*		Note: Self-administer (at home after administration of first dose of each new dose level in the clinic). Study drug is not to be taken on the day of an Exit DBPCFC. + EOT drug administration will occur as part of the Open-label extension study *If needed.
In-clinic observation post– study drug administration		X	X				X*		Subject to be observed for a minimum of 2 hours after initial study drug administration and after every initial updosing to a new dose level. *Refer to Section 6.5.2 for dose modifications.
Dispense/return study drug		X	X	X	X*		X#		*Return only. #If needed.
Telephone follow-up			X	X					Note: One day after each updosing visit, to inquire about allergic symptoms and promote adherence to treatment and remind subjects to complete the daily diary.
Assess eligibility for the OLE				X					Note: If not continuing to OLE, subjects will need counseling for withdrawing from study drug.
PEESS (pediatric) or EEsAI (adults)	G + 1T			D 1			X		If clinically indicated in event of suspicion of EoE

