7.7. Study Drug Exposure

Descriptive statistics for treatment exposure will be presented using the Safety Population. The treatment exposure will be summarized for pre-maintenance period, maintenance period, Exit Food Challenge/Week 40 Visit period, EOT and overall treatment period. The analysis will be repeated using ITT and PP Population if sufficiently different from Safety Population by more than 5% of study subjects. The following will be summarized:

- The treatment exposure (days) using exposure duration.
- The treatment exposure (days) by dose level using exposure duration.
- Cumulative dose of the study treatment (mg).
- The average daily dose of study treatment (mg)
- The number and percent of subjects with 1, 2, 3 or more unsuccessful dose increases (as defined in Section 6.2.6.2) during the pre-maintenance period.
- The number and percent of subjects with 1, 2, 3 or more dose decreases during the pre-maintenance period and/or the maintenance period.
- The number and percent of subjects with missing dose and the number of subjects with 1, 2, 3, ≥ 4 – ≤ 7 , or > 7 doses missed.

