7.9.1. Adverse Events

All AEs will be coded and classified according to MedDRA version 23.0 or later. All nonallergic AEs will be graded according to the NCI CTCAE Version 5.0. All allergic AEs will be graded according to the Consortium of Food Allergy Research (CoFAR) grading scale, with Grade 1 (mild symptoms), Grade 2 (moderate symptoms), Grade 3 (severe symptoms), Grade 4 (life-threatening symptoms) and Grade 5 (death). The relationship of AE to study drug will be judged by the investigator as related or not related.

Treatment-emergent AEs (TEAE) are defined as any event that starts or worsens in severity on or after the first dose of study drug until 30 days after the last dose of study drug. TEAEs will be considered treatment-related if relationship information is missing. Similarly, TEAEs will be considered severe if the severity information is missing. Imputed values for relationship, severity or onset date will be used for incidence summaries, while the actual values will be used in data listings. The AEs not considered to be a TEAE will be included in subject listings, but not summarized.

The AESIs include the following categories: anaphylaxis, any AE leading to the use of epinephrine (e.g., EAI), and Eosinophilic Esophagitis (EoE).

All reported AEs will be classified into SOC and PT. Summaries will be ordered by descending incidence of SOC and PT within each SOC for the overall column. Summaries displayed by PT only will be ordered by descending incidence of PT for the overall column. In addition, exposure adjusted incidence rates of TEAEs, treatment-emergent serious adverse events (TESAEs) and treatment-emergent AESIs will be presented, where exposure incidence rate is defined as the total number of events divided by the total number of subject-years at risk during the study treatment period, or defined as the total number of events divided by the total number of study drug doses received during the study treatment period.

An overview summary of the number and percentage of subjects with at least one of the following AE categories will be presented by treatment group and overall.

- Any TEAE
- Any TESAE
- Any TEAE related to study drug

- Any TEAE due to accidental exposure
- Any TEAE due to food challenge
- Any TEAE due to other study procedure
- Any TESAE related to study drug
- Any TESAE due to accidental exposure
- Any TESAE due to food challenge
- Any TESAE due to other study procedure
- Any TEAE resulting in drug discontinuation

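### SAP 6.2.6.1 leaves the only day-by-day record of home dosing out of the report, and no rule replaces it for missed doses, cumulative dose or AEs per dose received

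*SAP*

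**What the plan says.** SAP 6.2.6.1 states that exposure is not captured on the eCRF and names two external sources. The first is "Study drug_accountability (in-clinic) data from Suvoda IRT system". The second is "Subject daily dosing diary data (non-clinic data) via mobile application (mApp) managed by AiCure". Of the second it says: "This data will be sent directly to Alladapt for exploratory analysis and are not planned to be included in the CSR of this study". It then sets the basis for reporting: "The main calculation of exposure will be based on in-clinic dosing data and the dose level of the dispensed study drug", taken from the IRT system.

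Every duration in SAP 6.2.6.1 is a last date minus a first date plus one. Intervals at a dose level are split only where down dosing breaks them up. No formula deducts a missed dose, an AE hold or a day withheld for an Exit challenge.

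SAP 7.7 nevertheless lists cumulative dose, average daily dose and "The number and percent of subjects with missing dose", banded as 1, 2, 3, 4 to 7, and more than 7. SAP 7.9.1 defines one form of exposure-adjusted rate as the "total number of events divided by the total number of study drug doses received during the study treatment period". That form is planned for TEAEs, related TEAEs, serious TEAEs, AESIs and related AESIs, and by study period for TEAEs and AESIs. Neither section gives a derivation or a further data source.

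On the protocol side, the Schedule of Activities says: "The diary is intended to capture dose compliance and dosing-related symptoms that may occur". It also has subjects dose themselves at home once the first dose of each new level has been given in clinic. Protocol 6.1 asks for all containers back, used or not, and Protocol 6.4 assesses compliance from returned unused drug.

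**The concern.** The plan promises outputs that depend on knowing which home doses were taken, and sets aside the one record that says so day by day. If the listed sources are followed literally, a subject who misses several days between two visits looks continuously dosed at the dispensed level.

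Two kinds of output are at stake. The missed-dose summary uses the same bands as Protocol Table 4, which governs how gaps are handled, so a reader will take it as the account of adherence to those rules. The per-dose AE rates are a safety output of obvious interest for a daily oral immunotherapy. An inflated denominator makes reactions per dose look rarer than they were. If interruptions are commoner on ADP101, which is plausible because reactions can lead to holds (Protocol 6.5.2), the excess over placebo would shrink as well.

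**Working it through.** There is no stated figure to reproduce. The check traces each planned output to its source and then sizes the effect.

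**1. Share of doses taken at home.** Protocol Table 3 has 9 levels to 1500 mg and 11 to 4500 mg. Treatment before the Exit challenges is 40 × 7 = 280 days. With one clinic dose per level and no delays:
- Low regimen: 280 − 9 = 271 home doses; 271/280 = 96.8%.
- High regimen: 280 − 11 = 269 home doses; 269/280 = 96.1%.

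Repeat supervised doses after failed updosing, gaps or reactions would lower these shares somewhat.

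**2. What each record can show.** Gap handling is from Protocol Table 4.

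| Consecutive missed doses | Clinic dosing and dispensed level (SAP basis) | Returned units (collected, no SAP rule) | Diary (collected, outside the CSR) |
|---|---|---|---|
| 1–2 | No trace; dosing resumes at home | Total per dispensing interval | Dates and run |
| 3 | A supervised site dose, which does not date the gap | Total per interval | Dates and run |
| 4–7 | A reduced dose at the site, seen as a level change | Total per interval | Dates and run |
| More than 7 | Possible discontinuation under the individual stopping rules | Total per interval | Dates and run |

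Returned units can therefore correct totals but cannot separate one run of four from four single misses. Only the diary can.

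**3. Effect on per-dose rates.** Suppose all D days in the span are counted as doses, a fraction f was not taken, and E events occurred. The reported rate is E/D, the true rate is E/[D(1 − f)], and reported/true = 1 − f. The documents give no value of f; these are assumptions:
- f = 5%: reported/true 0.95; the true rate is 1/0.95 − 1 = 5.3% higher.
- f = 10%: 0.90; 11.1% higher.
- f = 15%: 0.85; 17.6% higher.

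The ADP101-to-placebo rate ratio is multiplied by (1 − f_active)/(1 − f_placebo). With assumed pairs of 5% and 2%, 10% and 3%, and 15% and 5%:
- 0.95/0.98 = 0.97
- 0.90/0.97 = 0.93
- 0.85/0.95 = 0.89

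Equal missing in both arms leaves the ratio unbiased. More missing on placebo would reverse the direction.

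**4. A case that stays inside the protocol's rules.** Three separate 7-day gaps trigger neither individual missed-dose stopping rule in Protocol 7.1.2: there are fewer than four occasions of four or more days, and no run exceeds seven. That is 21 doses, 21/280 = 7.5%, and the true per-dose rate is 280/259 − 1 = 8.1% above the reported one.

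Perfect-adherence cumulative dose, with 14 days per level before target:
- Low: 14 × 2475 + 168 × 1500 = 286,650 mg.
- High: 14 × 6975 + 140 × 4500 = 727,650 mg.

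If all 21 misses fall at target dose and none is deducted, the overstatement relative to the true dose is:
- Low: 21 × 1500 = 31,500 mg; 31,500/255,150 = 12.3%.
- High: 21 × 4500 = 94,500 mg; 94,500/633,150 = 14.9%.

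**5. Withheld days.** Drug is withheld on each Exit challenge day, with further days at the investigator's judgment (Protocol 4.1). The SAP duration for that period still runs from first to last dose.

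**The case against.** A reader might infer that home doses are recorded nowhere but the diary. The documents do not support that. Returned containers and unused drug are collected, and accountability is the SAP's first exposure source.

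A reader might also infer that the SAP counts missed doses as taken, or that the missed-dose table would falsely show almost no gaps. Neither is stated. The first-to-last formulas define durations. Cumulative dose, missed doses and doses received have no formula, calling the IRT-based calculation the main one leaves room for a returned-unit correction, and variable specifications sit in a separate document (SAP 11). The bands are not said to be consecutive; if they are totals, dispensed minus returned could fill them. Nor would the table rest only on the 9 or 11 first-of-level clinic doses, because gaps of three or more should lead to a site dose, a reduced dose or the stopping rules.

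Other mitigating points are fair. TEAEs leading to interruption are summarised, and those AEs are listed. The SAP acknowledges Exit-challenge withholding. Per-dose rates are descriptive and sit beside person-year rates and subject incidence.

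All of this stands and limits the claim. It does not remove it. No SAP rule uses returned counts, gaps of one or two doses leave no site trace, and the exposure formulas do not subtract AE holds even though the AE tables flag them. Leaving the diary out is an explicit decision, not a missing detail.

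**Conclusion.** The point holds as a defect in specification and choice of data source. SAP 6.2.6.1 excludes the only dated, dose-by-dose record of home dosing (about 96–97% of doses to Week 40 with uninterrupted updosing), and SAP 7.7 and 7.9.1 supply no alternative derivation. Following the stated sources, short home gaps would be invisible, longer ones would show only indirectly, and per-dose AE rates would tend to be understated by the missed fraction.

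The size is unknown. The 5–15% range and any between-arm difference are assumptions, and the tendency to understate presumes that span days at the dispensed level are counted as doses, which is the natural reading but not stated text. Person-year rates and the primary and secondary efficacy analyses do not depend on it. It should be corrected before database lock, because the affected outputs describe safety and adherence and the better data are already collected.

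**What to change.** In SAP 6.2.6.1:
- Define doses received per dispensing interval as dispensed minus returned units, converted to daily doses, since Protocol 6.1 lists several unit strengths. State what happens when containers are not returned.
- Exclude doses documented as held for AEs or withheld for Exit challenges, subtracting each once if it also came back as a returned unit.
- Use the diary to date missed doses and derive consecutive runs. Where the diary has no entry, use the dispensed-minus-returned total for that interval. Do not fall back on the assumption that the dose was taken, because skipped doses and skipped entries may well coincide.

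In SAP 7.7, state whether the missed-dose bands are totals or consecutive runs, and base them, cumulative dose and average daily dose on these counts. In SAP 7.9.1, use the same count as the per-dose denominator and show the IRT-only figure alongside.

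If the diary is still kept out of the CSR, the minimum is to specify the dispensed-minus-returned derivation and limit the missed-dose table to totals per interval.

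The cost is mainly programming, since the diary data already go to the sponsor. The downside is incomplete diary entries, so some runs will stay undated; report how many days lack an entry, by arm.

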6.2.6.2. Unsuccessful Dose Increase

An unsuccessful dose increase is defined as a single dose at a higher dose level, followed by a return to the previous dose level (or a lower level).

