6.5. Updosing and Dose Modifications of Study Drug

6.5.1. Updosing and Downdosing of Study Drug

Initial updosing to a new level will be attempted sequentially every 2 weeks per the updosing regimens in Table 3. A telephone call follow-up will be done 1 day after each updosing visit to inquire about allergic symptoms and promote adherence to treatment, and remind subjects to complete the daily diary. As shown in Table 5, subjects who fail to tolerate dose levels of at least 50 mg/day will discontinue study drug; these subjects will remain in the study per Section 7.2.

Subjects who tolerate at least 50 mg/day will continue in the updosing portion of the study, and will return to the clinic every 2 weeks for updosing under direct medical supervision until the randomized target dose of 1500 mg/day (100 mg per food source; low-dose regimen) or 4500 mg/day (300 mg per food source; high-dose regimen) is achieved (Figure 1). If a subject fails 3 updosing attempts to any dose level above 50 mg/day, the site should contact the Study Medical Monitor for further guidance regarding additional updosing. Subjects who are unable to reach the randomized target dose will continue on the highest dose level they are able to reach, as long as the dose of study drug is at least 50 mg.

Subjects who do not tolerate the current dose level may be permitted to downdose to a previous dose level at the discretion of the investigator.

Subjects must not be updosed for 3 days after the cessation of administration of corticosteroids.

For guidance regarding updosing during a public health emergency, refer to Appendix 6 (Section 10.6).

Table 5: Updosing Decisions for Study Drug

Dose Level Attempted during Updosing Phase (mg)	Tolerated Dose within 3 Attempts?	Instructions
5	Yes	Continue to the next dose level.
	No	Discontinue study drug and remain in the study per Section 7.2. An additional subject will be randomized without impacting the overall 2:2:1:1 randomization ratio.
20	Yes	Continue to the next dose level.
	No	Discontinue study drug and remain in the study per Section 7.2.
50	Yes	Continue to the next dose level; subject is eligible to continue the study.
	No	Discontinue study drug and remain in the study per Section 7.2.
Any dose above	Yes	Continue to the next dose level.
50 mg	No	Contact Study Medical Monitor for further instructions.

In-Clinic Observation after Initial Study Drug Administration and Every Updosing

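### A failed updose that ends in permanent discontinuation is not counted as an unsuccessful dose increase under SAP 6.2.6.2

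*SAP*

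**What the plan says.** SAP 6.2.6.2 gives the definition: "An unsuccessful dose increase is defined as a single dose at a higher dose level, followed by a return to the previous dose level". A return to a level lower still also qualifies. SAP 7.7 applies it in the exposure summary: "The number and percent of subjects with 1, 2, 3 or more unsuccessful dose increases (as defined in Section 6.2.6.2) during the pre-maintenance period". The same list has a separate row for reductions: "The number and percent of subjects with 1, 2, 3 or more dose decreases during the pre-maintenance period", extending also to maintenance. That row has no single-dose condition.

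Protocol 6.5.1 and Table 5 judge an updose by whether the level was tolerated within three attempts. At 20 mg and 50 mg the instruction after failure is "Discontinue study drug and remain in the study per Section 7.2". At 5 mg study drug is also stopped, and another subject is randomized. Above 50 mg the route differs: "If a subject fails 3 updosing attempts to any dose level above 50 mg/day, the site should contact the Study Medical Monitor". A subject who cannot reach target then stays on the highest level reached, provided that it is at least 50 mg. Protocol Table 6 lists permanent discontinuation as the action for a Grade 4 allergic reaction.

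**The concern.** The definition needs two things together: exactly one dose at the new level, and a later dose at the old level or below. A subject whose failed updose is also the last dose of study drug has no later dose, so the second condition cannot be met. The attempts left out are therefore those that ended treatment.

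I found no other count of failed updosing attempts in the SAP. A subject stopped after three failures at 20 mg or 50 mg can sit in the category for two, and a subject stopped at a first failed updose can appear to have had none. Safety and tolerability are a stated objective, so the table should not lose these events through its wording.

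**Working it through.** The plan gives no figure that depends on this definition, so there is nothing to reproduce. The check applies the rule to dosing records built from Protocol Tables 3, 5 and 6.

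**Rule as written.** Treat a record as successive runs at one level. Run *i* counts if all three hold:

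- level(*i*) > level(*i*−1)
- doses in run *i* = 1
- level(*i*+1) ≤ level(*i*−1)

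If study drug stops after run *i*, level(*i*+1) does not exist and the third condition fails.

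**Assumptions.** Each failed attempt is one in-clinic dose unless stated, and the subject goes back to the previous level between attempts.

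**Worked record, 20 mg:** 5 → 20 (1 dose) → 5 → 20 (1 dose) → 5 → 20 (1 dose) → stopped. The first two attempts count and the third does not, so the score is 2.

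| Record | Score as written | Score if discontinuation also completes the event |
|---|---|---|
| Three failures at 20 mg, then stopped | 2 | 3 |
| Three failures at 50 mg, then stopped | 2 | 3 |
| One failure at 20 mg, later three at 50 mg, then stopped | 1 + 2 = 3 | 4 |
| Three failures at one level from 100 to 4500 mg, continues lower | 3 | 3 |
| Three failures at 100 mg, stopped after the third | 2 | 3 |
| First failed updose, stopped at once (e.g. Grade 4) | 0 | 1 |
| Three failures at 5 mg, then stopped | 0 (no increase) | 0 |
| Three failures at 20 or 50 mg, each after one home dose, then stopped | 0 (2 dose decreases) | 0 |
| Three failures at one level above 50 mg, each after one home dose, continues lower | 0 (3 dose decreases) | 0 |

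**Size per affected subject.** Planned numbers come from Protocol Table 1 and SAP Table 1.

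- All subjects, one ADP101 arm: 1/24 = 4.2 percentage points.
- Pediatric table, one ADP101 arm: 1/20 = 5.0 percentage points.
- Pooled placebo has the same denominators: 12 + 12 = 24, and 10 + 10 = 20.

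For a subject stopped under the three-attempt rule at 20 or 50 mg with no earlier counted failure, the shift is from the category for two to the category for three or more. The number with at least one unsuccessful increase does not change. For a subject stopped at a first failed updose, the shift is from none to one.

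**The case against.** The strongest reply is that this is one descriptive exposure row and that the events are reported elsewhere. SAP 7.1 gives treatment termination with its primary reason. SAP 7.9.1 gives TEAEs leading to discontinuation, interruption or modification of study drug. SAP 7.8.3.10 and 7.8.3.11 give the maintenance dose, target attainment by visit and a swimmer plot by dose level. No endpoint, test or sample size uses the row. All of this stands, and it limits the importance of the point. But those tables show that treatment stopped, not how many updosing attempts failed, so they do not correct the count.

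The programming specifications and table shells (SAP Sections 11 and 12) are separate documents and may handle the case. They were not available, and the SAP text as written excludes it.

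A reader might infer more than the documents support:

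- **That anyone who meets the three-attempt rule is scored 2.** Table 3 has 11 levels, of which 8 are above 50 mg. There the protocol provides for continuing on the highest level reached, which gives 3. At 5 mg the score is 0 because nothing was increased. At 50 mg, one earlier counted failure brings the score to 3.
- **That the three-or-more category reproduces the protocol's rule.** SAP 7.7 counts over the whole pre-maintenance period, Table 5 counts at one level, and the SAP does not link them.
- **That severe reactions in general are missed.** For Grade 3, Table 6 lists holding and reducing the dose before discontinuation, so that route normally includes a return and the attempt can count. Immediate permanent discontinuation is listed for Grade 4.
- **That failures after home doses are lost.** They fail the single-dose condition, but a resulting reduction appears in the dose-decrease row.
- **That the ADP101-placebo difference is understated.** This needs terminal failures to be more frequent on ADP101, and the documents give no such counts.

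**Conclusion.** The point holds in a limited form. As written, SAP 6.2.6.2 omits any failed updose that ends in permanent discontinuation. The score is 2 instead of 3 after three failures at 20 mg or at 50 mg with no earlier counted failure, and 0 instead of 1 when treatment stops at a first failed updose. Above 50 mg the count is right when the subject continues at a lower level, and 5 mg failures are outside the definition.

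The size is 4.2 percentage points per affected subject in an ADP101 arm, or 5.0 in the pediatric table. This rests on the planned arm sizes and on each failed attempt being a single clinic dose. How many subjects are affected, and in which arm, cannot be known from the documents. The definition deserves correction because it drops treatment-ending attempts and the repair is cheap, but no efficacy or safety conclusion turns on it.

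**What to change.** Extend SAP 6.2.6.2 so that one dose at a higher level counts when it is followed either by a return to the previous or a lower level, as now, or by permanent discontinuation of study drug. The terminal case can be identified by matching the in-clinic updosing date in the IRT data with the last administration date on the EOT eCRF. Add a row to the SAP 7.7 summary for attempts ending in discontinuation. The primary reason for termination on the EOT eCRF would show which of these stops were unrelated to tolerability.

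Leave reductions after home dosing in the dose-decrease row. A wider definition based on intolerance would need a reason for each change of dose. SAP 6.2.6.1 does not say that the IRT data hold one, and the home diary is not planned for the CSR. A stop after two or more doses at a new level would therefore stay outside this count and be seen only in the disposition and AE tables.

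The cost is a short SAP amendment and a small amount of programming. No dosing or stopping rule changes.
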